### **6.13.3. Vital Signs and Other Physical Findings**

For the treatment-emergent categorical analyses (shift and treatment-emergent), the analysis period is defined as the treatment period plus up to 30 days off-drug follow-up time. The

analysis period for the continuous analyses (for example, change from baseline by time point) is defined as the treatment period excluding off-drug follow-up time.

Vital signs and physical characteristics include systolic blood pressure (SBP), diastolic blood pressure (DBP), pulse, weight, and BMI. Original-scale data will be analyzed. When these parameters are analyzed as continuous numerical variables, unplanned measurements will be excluded. When these parameters are analyzed as categorical outcomes and/or treatment-emergent abnormalities, planned and unplanned measurements will be included.

The planned analyses described for the laboratory analytes in Section 6.13.2 will be used to analyze the vital signs and physical characteristics.

Table JAIN.6.10 defines the low and high baseline values as well as the criteria used to define treatment-emergence based on postbaseline values. The blood pressure and pulse rate criteria are consistent with the document *Selected Reference Limits for Pulse/Heart Rate, Arterial Blood Pressure (Including Orthostasis), and Electrocardiogram Numerical Parameters for Use in Analyses of Phase 2-4 Clinical Trials Version 1.3* approved on April 29, 2015 as recommended by the Lilly Cardiovascular Safety Advisory Committee (CVSAC).

**Table JAIN.6.13. Categorical Criteria for Abnormal Treatment-Emergent Blood Pressure and Pulse Measurement and Categorical Criteria for Weight Changes for Adults**

Parameter (Units of Measure)	Low	High
Systolic Blood Pressure (mm Hg)	$\leq 90$ (low limit) and decrease from lowest value during baseline $\geq 20$ if $>90$ at each baseline visit	$\geq 140$ (high limit) and increase from highest value during baseline $\geq 20$ if $<140$ at each baseline visit
Diastolic Blood Pressure (mm Hg)	$\leq 50$ (low limit) and decrease from lowest value during baseline $\geq 10$ if $>50$ at each baseline visit	$\geq 90$ (high limit) and increase from highest value during baseline $\geq 10$ if $<90$ at each baseline visit
Pulse (beats per minute)	$<50$ (low limit) and decrease from lowest value during baseline $\geq 15$ if $\geq 50$ at each baseline visit	$>100$ (high limit) and increase from highest value during baseline $\geq 15$ if $\leq 100$ at each baseline visit
Weight (kilograms)	(Loss) decrease $\geq 7\%$ from lowest value during baseline	(Gain) increase $\geq 7\%$ from highest value during baseline

#### **6.13.4. Special Safety Topics, including Adverse Events of Special Interest**

In addition to general safety parameters, safety information on specific topics of special interest will also be presented. Additional special safety topics may be added as warranted. The topics outlined in this section include the protocol-specified AESI.

In general, for topics regarding safety in special groups and circumstances, patient profiles and/or patient listings, where applicable, will be provided when needed to allow medical review of the time course of cases/events, related parameters, patient demographics, study drug treatment and meaningful concomitant medication use. In addition to the safety topics for which

provision or review of patient data is specified, these will be provided when summary data are insufficient to permit adequate understanding of the safety topic.

#### 6.13.4.1. Abnormal Hepatic Tests

Analyses for abnormal hepatic tests will involve 4 laboratory analytes: ALT, AST, total bilirubin, and ALP. In addition to the analyses described in Section 6.2.2.2, this section describes specific analyses for this topic.

First, the number and percentage of patients with the following abnormal elevations in hepatic laboratory tests at any time will be summarized between treatment groups:

- The percentages of patients with an ALT measurement  $\geq 3\times$ ,  $5\times$ , and  $10\times$  the central laboratory upper limit of normal (ULN) during the treatment period will be summarized for all patients with a postbaseline value and for subsets based on various baseline values.
  - The analysis of  $3\times$  ULN will contain 4 subsets: patients whose non-missing maximum baseline value is  $\leq 1\times$  ULN, patients whose maximum baseline is  $>1\times$  ULN but  $<3\times$  ULN, patients whose maximum baseline value is  $\geq 3\times$  ULN, and patients whose baseline values are missing.
  - The analysis of  $5\times$  ULN will contain 5 subsets: patients whose non-missing maximum baseline value is  $\leq 1\times$  ULN, patients whose maximum baseline is  $>1\times$  ULN but  $<3\times$  ULN, patients whose maximum baseline is  $\geq 3\times$  ULN but  $<5\times$  ULN, patients whose maximum baseline value is  $\geq 5\times$  ULN, and patients whose baseline values are missing.
  - The analysis of  $10\times$  ULN will contain 6 subsets: patients whose non-missing maximum baseline value is  $\leq 1\times$  ULN, patients whose maximum baseline is  $>1\times$  ULN but  $<3\times$  ULN, patients whose maximum baseline is  $\geq 3\times$  ULN but  $<5\times$  ULN, patients whose maximum baseline is  $\geq 5\times$  ULN but  $<10\times$  ULN, patients whose maximum baseline value is  $\geq 10\times$  ULN, and patients whose baseline values are missing.
- The percentages of patients with an AST measurement  $\geq 3\times$ ,  $5\times$ , and  $10\times$  the central laboratory ULN during the treatment period will be summarized for all patients with a postbaseline value and for subsets based on various levels of baseline. Analyses will be constructed as described above for ALT.
- The percentages of patients with a total bilirubin measurement  $\geq 2\times$  the central laboratory ULN during the treatment period will be summarized for all patients with a postbaseline value and subset into 4 subsets: patients whose non-missing maximum baseline value is  $\leq 1\times$  ULN, patients whose maximum baseline is  $>1\times$  ULN but  $<2\times$  ULN, patients whose maximum baseline value is  $\geq 2\times$  ULN, and patients whose baseline values are missing.
- The percentages of patients with an ALP measurement  $\geq 1.5\times$  the central laboratory ULN during the treatment period will be summarized for all patients with a postbaseline value and subset into 4 subsets: patients whose non-missing maximum baseline value is  $\leq 1\times$  ULN, patients whose maximum baseline is  $>1\times$  ULN but  $<1.5\times$  ULN, patients whose maximum baseline value is  $\geq 1.5\times$  ULN, and patients whose baseline values are missing.

Information collected from additional hepatic safety data collection forms will be provided in patient profiles.

Second, to further evaluate potential hepatotoxicity, an Evaluation of Drug-Induced Serious Hepatotoxicity (eDISH) plot using maximum postbaseline ALT divided by ULN versus maximum postbaseline total bilirubin divided by ULN will be created that includes all patients from the safety populations for the studies included in the submission (any phase, any medication). Each patient with at least 1 postbaseline ALT and total bilirubin contributes 1 point to the plot. The measurements do not need to be taken at the same blood draw. Symbols will be used to indicate randomized treatment.

When criteria are met for hepatic evaluation and completion of the hepatic safety case report form (CRF), investigators are required to answer a list of questions (see the Compound level safety standards). A listing of this collected information will be generated together with a graphical patient profile. This includes demographics, disposition, and a display of study drug exposure, AEs, medications, and the liver-related measurements over time will be provided for these patients and any additional patients meeting ALT or AST measurement greater than or equal to  $5 \times$  ULN (on a single measurement) or ALP measurement greater than or equal to  $2 \times$  ULN (on a single measurement).

#### **6.13.4.2. Hematologic Changes**

Hematologic changes will be defined based on clinical laboratory assessments. Common Terminology Criteria for Adverse Events (CTCAEs) will be applied for selected laboratory tests and are described in the Compound level safety standards. These CTCAE grading schemes are consistent with both Version 3.0, Version 4.03, and Version 5 of the CTCAE guidelines (CTCAE 2003, 2010, 2017).

Treatment-emergent laboratory abnormalities occurring at any time during the treatment period and shift tables of baseline to maximum grade during the treatment period will be tabulated. Planned and unplanned measurements will be included. Treatment-emergence will be characterized using the following 5 criteria (as appropriate to the grading scheme):

- any increase in postbaseline CTCAE grade from worst baseline grade
- increase to Grade 1 or above at worst postbaseline
- increase to Grade 2 or above at worst postbaseline
- increase to Grade 3 or above at worst postbaseline
- increase to Grade 4 at worst postbaseline

Shift tables will show the number and percentage of patients based on baseline to maximum during the treatment period, with baseline depicted by the most extreme grade during the baseline period. With each shift table, a shift table summary displaying the number and percentage of patients with maximum postbaseline results will be presented by treatment group for each treatment period within the following categories:

- Decreased: postbaseline category  $<$  baseline category
- Increased: postbaseline category  $>$  baseline category

- Same: postbaseline category = baseline category

A laboratory-based treatment-emergent outcome related to increased platelet count will be summarized in similar fashion. Treatment-emergent thrombocytosis as a laboratory-based abnormality will be defined as an increase in platelet count from a maximum baseline value  $\leq 600$  billion/L to any postbaseline value  $> 600$  billion/L (Lengfelder et al. 1998). In addition, increase in platelet count from a maximum baseline value  $\leq 400$  billion/L to any postbaseline value  $> 400$  billion/L will be derived and analyzed. Planned and unplanned measurements will be included.

A listing of patients with treatment-emergent thrombocytosis may be provided for safety review.

#### **6.13.4.3. Lipid Effects**

Lipid effects will be assessed through analysis of elevated total cholesterol, elevated LDL cholesterol, decreased HDL cholesterol, and elevated triglycerides as described in Section 6.13.2 and with TEAEs potentially related to hyperlipidemia.

Categorical analyses will be performed using National Cholesterol Education Program (NCEP) Adult Treatment Panel (ATP) III guidelines (2002) as shown in the Compound level safety standards. The grade-like categories shown in this table are ordered from traditionally most desirable to least desirable for the purposes of these analyses.

Shift tables will show the number and percentage of patients based on baseline to the least desirable category during the treatment period, with baseline depicted by the least desirable category during the baseline period. With each shift table, a shift table summary displaying the number and percentage of patients with the least desirable postbaseline results will be presented by treatment group for each treatment period within the following categories:

- Decreased: postbaseline category more desirable than baseline category
- Increased: postbaseline category less desirable than baseline category
- Same: postbaseline category = baseline category

Treatment-emergent laboratory abnormalities related to elevated total cholesterol, elevated triglycerides, elevated LDL cholesterol, and decreased and increased HDL cholesterol occurring at any time during the analysis period will be tabulated using the NCEP categories shown in the Compound level safety standards.

Treatment-emergent elevated total cholesterol will be characterized as follows:

- increase to categories 'Borderline high' or 'High'
- increase to category 'High'

Treatment-emergent elevated triglycerides will be characterized as

- increase to categories 'Borderline high,' 'High,' or 'Very high'
- increase to categories 'High' or 'Very high'
- increase to category 'Very high'

Treatment-emergent elevated LDL cholesterol will be characterized as

- increase to categories ‘Borderline high,’ ‘High,’ or ‘Very high’
- increase to categories ‘High’ or ‘Very high’
- increase to ‘Very high’

Treatment-emergent abnormal HDL cholesterol will be characterized as

- decreased
  - decrease to categories ‘Normal’ or ‘Low’
  - decrease to category ‘Low’
- increased
  - increase to categories ‘Normal’ or ‘High’
  - increase to category ‘High’.

The percentages of patients with treatment-emergent potential hyperlipidemia will be summarized by treatment group, ordered by decreasing frequency in the All baricitinib group using a predefined MedDRA list of PTs that is a subset of the narrow scope PTs in the MedDRA SMQ ‘Dyslipidemia’ (code 200000026) [see Compound level safety standards].

#### **6.13.4.4. Renal Function Effects**

Effects on renal function will be assessed through analysis of elevated creatinine.

Common Terminology Criteria for Adverse Events will be applied for laboratory tests related to renal effects as shown in the Compound level safety standards.

Shift tables will show the number and percentage of patients based on baseline to maximum during the analysis period, with baseline depicted by highest grade during the baseline period. Treatment-emergent laboratory abnormalities related to elevated creatinine occurring at any time during the treatment period will be tabulated. Refer to the Compound level safety standards for details.

#### **6.13.4.5. Elevations in Creatine Phosphokinase**

Elevations in CPK will be addressed using CTCAE criteria as shown in the Compound level safety standards. A listing of elevated CPK (CTCAE Grade of 3 or above) may be provided for medical safety review.

Treatment-emergent adverse events potentially related to muscle symptoms may be analyzed based on reported AEs. The Muscle Symptoms special search category is a predefined MedDRA search criteria list that contains the narrow scope terms from the Rhabdomyolysis/myopathy SMQ (code 20000002) plus selected terms from the Musculoskeletal SOC. These terms are shown in the Compound level safety standards.

#### **6.13.4.6. Infections**

Infections will be defined using all the PTs from the Infections and Infestations SOC as defined in MedDRA. Serious infection will be defined as all the infections that meet the SAE criteria.

The number and percentage of patients with TEAEs of infections, serious infections, and infections resulting in permanent study drug discontinuation will be summarized by treatment

group using MedDRA PTs. The proportion of patients developing skin infections requiring antibiotic treatment by Week 16 and end of study will also be summarized on the overview of infections table.

The number and percentage of patients with TEAEs of infections by maximum severity will be summarized by treatment group using MedDRA PTs.

The IR and 95% CI will be calculated for infections of special interest (serious infections, treatment-emergent herpes zoster, treatment-emergent tuberculosis, treatment-emergent opportunistic infections) for the Week 52 and final analyses.

Treatment-emergent infections will be reviewed in context of other clinical and laboratory parameters via a listing (details see Compound level safety standards).

The TEAE infections will be further analyzed in terms of potential opportunistic infection, herpes zoster, and herpes simplex. Summary of hepatitis B virus (HBV) deoxyribonucleic acid (DNA) monitoring results and association between infection and neutropenia/lymphopenia will also be provided in the context of infections.

### **Opportunistic Infection**

A list of PTs based on potential opportunistic infections spreadsheet provided by the Lilly Safety Standardization Team, and aligned with Winthrop et al. 2015, will be provided to medical for internal case review to define infections classified as opportunistic.

A final listing for OIs will be provided for the CSR and to assist in composition of patient narratives.

### **Herpes Zoster**

Cases of herpes zoster will be further classified as follows:

- localized or non-multidermatomal involvement of the primary and/or adjacent dermatomes only
  - complicated – documented ocular (cornea or deeper structure; eg, iritis, keratitis, retinitis, etc.) or motor nerve involvement (eg, palsy; postherpetic neuralgia does not meet criteria for motor nerve involvement)
  - uncomplicated-localized or non-multidermatomal cases that are not complicated
- multidermatomal – involvement beyond primary and adjacent dermatomes (that is, >3 contiguous dermatomes) or involvement of 2 or more non-contiguous dermatomes
  - complicated-document ocular (cornea or deeper structure; for example, iritis, keratitis, retinitis) or motor nerve involvement
  - uncomplicated-multidermatomal cases
- disseminated-systemic infection, visceral or widespread cutaneous (for example, ≥5 dermatomes or 3 to 4 dermatomes including at least 1 non-contiguous [non-adjacent])

All cases of herpes zoster will undergo medical review to determine the classification as described above.

A summary of herpes zoster table will be provided. The summary table will also include event maximum severity, seriousness, whether resulting in temporary study drug interruption, whether resulting in study drug discontinuation, whether treated with antiviral medication, and event outcome. Of note, in the context of herpes zoster, antiviral treatment is defined as that the follows: the medication was initiated at the event start date or within 30 days before or after the event start date. The antiviral medication for herpes zoster includes but is not limited to aciclovir, brivudine, cidofovir, famciclovir, foscarnet, ganciclovir, penciclovir, valaciclovir, valganciclovir, vidarabine (best presented by J05AB, J05AC, J05AE, and J05AH ATC codes). Medical representatives may review the concomitant medication list prior to the DBL and make adjustment of the above list if necessary.

If a patient has more than 1 event of herpes zoster, the event with the maximum severity will be used in these summary tables. If more than 1 event of herpes zoster occurs with the same severity, the event with the longest duration will be used in the summary table.

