### 6.13.1. Adverse Events

Adverse events are recorded in the eCRFs. Each AE will be coded to System Organ Class (SOC) and Preferred Term (PT) using the Medical Dictionary for Regulatory Activities

(MedDRA) version that is current at the time of DBL. Severity of AEs is recorded as mild, moderate, or severe.

A treatment-emergent adverse event (TEAE) is defined as an event that either first occurred or worsened in severity after the first dose of study treatment and on or prior to the last visit date during the analysis period. The analysis period is defined as the treatment period plus up to 30 days off-drug follow-up time.

Adverse events are classified based upon the MedDRA PT. The MedDRA Lowest Level Term (LLT) will be used in defining which events are treatment-emergent. The maximum severity for each LLT during the baseline period up to first dose of the study medication will be used as baseline. If an event with missing severity is pre-existing during the baseline period, and persists during the treatment period, then the baseline severity will be considered mild for determining treatment-emergence (that is, the event is treatment-emergent if the severity is coded moderate or severe postbaseline and not treatment-emergent if the severity is coded mild postbaseline). If an event occurring postbaseline has a missing severity rating, then the event is considered treatment-emergent unless the baseline rating is severe, in which case the event is not a treatment-emergent. The day and time for events where onset is on the day of the first dose of study treatment will both be used to distinguish between pretreatment and posttreatment to derive treatment-emergence. Should there be insufficient data for AE start date to make this comparison (for example, the AE start year is the same as the treatment start year, but the AE start month and day are missing), the AE will be considered treatment-emergent.

In general, summaries will include the number of patients in the safety population (N), frequency of patients experiencing the event (n), and relative frequency (that is, percentage;  $n/N*100$ ). For any events that are gender-specific based on the displayed PT, the denominator used to compute the percentage will only include patients from the given gender.

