#### **6.13.1.2. Serious Adverse Event Analyses**

Consistent with the International Conference on Harmonisation (ICH) E2A guideline (1994) and 21 Code of Federal Regulations (CFR) 312.32 (a) (2010), an SAE is any AE that results in any one of the following outcomes:

- Death
- Initial or prolonged inpatient hospitalization
- A life-threatening experience (that is, immediate risk of dying)
- Persistent or significant disability/incapacity
- Congenital anomaly/birth defect

Important medical events that may not be immediately life-threatening or result in death or hospitalization but may jeopardize the patient or may require intervention to prevent one of the other outcomes listed in the definition above should be considered as serious. See examples in the ICH E2A guideline Section 3B.

The number and percentage of patients who experienced any SAE will be summarized by treatment using MedDRA PT nested within SOC. Events will be ordered by decreasing frequency in the All baricitinib group within decreasing frequency in SOC. The SAEs will also be summarized by treatment using MedDRA PT without SOC.

An individual listing of all SAEs will be provided. A listing of deaths, regardless of when they occurred during the study, will also be provided.

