### 6.13.1.3. Other Significant Adverse Events

Other significant AEs to be summarized will provide the number and percentage of patients who

- permanently discontinued study drug because of an AE or death, and
- temporarily interrupted study drug because of AE

by treatment using MedDRA PT nested within SOC. Events will be ordered by decreasing frequency in the All baricitinib group within decreasing frequency in SOC.

A summary of temporary interruptions of study drug will also be provided, showing the number of patients who experienced at least 1 temporary interruption and the number of temporary interruptions per patient with an interruption. Further, the duration of each temporary interruption (in days), the cumulative duration of dose interruption (in days) using basic descriptive statistics, and the reason for dose interruption will be provided.

A listing of all AEs leading to permanent discontinuation from the study drug or from the study will be provided. A listing of all temporary study drug interruptions, including interruptions for reasons other than AEs, will be provided.

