### **Herpes Simplex**

A summary analysis of herpes simplex will be provided. Herpes simplex will be defined based on MedDRA PT as listed in Compound level safety standards (both narrow and broad terms in the herpes simplex section). The list is reviewed by GPS/medical prior to data locks (final and interim). The summary table will include event maximum severity, seriousness, whether resulting in temporary study drug interruption, whether resulting in study drug discontinuation, and whether treated with antiviral medication.

If a patient has more than 1 event of herpes simplex, the event with the maximum severity will be used in these summary tables. If more than 1 event of herpes simplex occurs with the same severity, the event with the longest duration will be used in the summary table.

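### Herpes zoster and simplex tables use one event per patient, so their yes/no rows (seriousness, interruption, discontinuation, antiviral use) can undercount patients and never overcount them

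*SAP*

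**What the plan says.** In the Herpes Zoster part of SAP section 6.13.4.6, the contents of the table are listed: "The summary table will also include event maximum severity, seriousness, whether resulting in temporary study drug interruption". The list continues with drug discontinuation, antiviral treatment and event outcome. The rule for patients with repeat events follows: "If a patient has more than 1 event of herpes zoster, the event with the maximum severity will be used in these summary tables". Events of equal severity are separated by duration, and the longest is used.

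The Herpes Simplex part lists the same rows except outcome and repeats the rule, including the tie-break: "If more than 1 event of herpes simplex occurs with the same severity, the event with the longest duration will be used".

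Four other places in the SAP bear on the point:

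- Section 6.13.1 defines the scale that drives the selection: "Severity of AEs is recorded as mild, moderate, or severe".
- Section 6.13.4.6 defines seriousness separately, across all infections: "Serious infection will be defined as all the infections that meet the SAE criteria". Serious infections and infections leading to permanent discontinuation are summarised there by preferred term, with no one-event rule.
- Section 6.13.1.2 counts patients with any SAE by preferred term and adds: "An individual listing of all SAEs will be provided". Section 6.13.1.3 does the same for discontinuations and interruptions due to AEs, and adds: "A listing of all temporary study drug interruptions, including interruptions for reasons other than AEs, will be provided".
- Section 6.13.4 offers event-level data conditionally: "patient profiles and/or patient listings, where applicable, will be provided when needed to allow medical review of the time course of cases/events". Section 6.13.4.6 also plans, without condition, a listing of treatment-emergent infections, but leaves its content to the Compound level safety standards.

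**The concern.** The variable that selects the event is not the variable being reported. A mild/moderate/severe grade does not determine whether an event met an SAE criterion, led to a dose hold, ended treatment or was treated with an antiviral. Duration, the tie-break, does not determine these either. Taking the most severe event is right for the maximum-severity row. For the four yes/no rows it can discard a yes, including one from an event that was equally severe but shorter. Nothing in either subsection says that these rows are taken across all of a patient's events.

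A reader is likely to take each row as the number of patients with that feature. Infections including herpes zoster are adverse events of special interest (Protocol section 9.2.2), and treatment can last up to 200 weeks, which leaves time for repeat episodes. At stake is the accuracy of a descriptive safety display. Patient incidence, the maximum-severity row and patients with a single event are unaffected, as are efficacy, alpha and the incidence rates.

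**Working it through.** The plan states no figure here, so there is none to reproduce.

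**1. Does the rule lose information?** Take two constructed patients with two events each.

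- Patient A: a severe 20-day event with no features, and a moderate 10-day event that was serious, interrupted drug, ended treatment and was treated with an antiviral.
- Patient B: two moderate events, a 30-day one with no features and a 7-day one that interrupted drug and was treated.

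| Row | SAP rule | Any event |
|---|---|---|
| Serious | 0 | 1 |
| Interruption | 0 | 2 |
| Discontinuation | 0 | 1 |
| Antiviral | 0 | 2 |

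The selected event is one of the patient's events, so the count under the rule can never exceed the any-event count.

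**2. How large could it be?** From the Protocol: 200 patients planned on 2 mg and 100 in each other arm. Everything else is assumed:

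- two events per recurrent patient;
- severity mix 50/40/10% mild/moderate/severe;
- zoster in 3–6% of patients, 5–10% of them recurrent;
- simplex in 5–15%, 20–40% of them recurrent;
- share of events with the feature: serious 5%, zoster antiviral 80%, simplex antiviral 50%.

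Ties on severity: 0.5² + 0.4² + 0.1² = 0.42, so 42% of pairs are decided by duration alone.

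Recurrent patients in the 2-mg arm:

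- zoster: 200 × 0.03 × 0.05 = 0.3 to 200 × 0.06 × 0.10 = 1.2
- simplex: 200 × 0.05 × 0.20 = 2 to 200 × 0.15 × 0.40 = 12

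Loss per recurrent patient, for a feature carried by a share p of events:

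- High end (feature unrelated to severity, independent between events): [1 − (1 − p)²] − p = p(1 − p). This gives 0.0475 at 5%, 0.16 at 80% and 0.25 at 50%.
- Low end (feature placed in the most severe events first): serious 0.0975 − 0.095 = 0.0025; zoster antiviral 0.96 − 0.90 = 0.06; simplex antiviral 0.75 − 0.75 = 0.

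Expected shortfall in patients, 2-mg arm (halve for the 100-patient arms):

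| Row | Low | High |
|---|---|---|
| Zoster, serious | 0.3 × 0.0025 = 0.00075 | 1.2 × 0.0475 = 0.057 |
| Zoster, antiviral | 0.3 × 0.06 = 0.018 | 1.2 × 0.16 = 0.192 |
| Simplex, serious or any other 5% feature | 2 × 0.0025 = 0.005 | 12 × 0.0475 = 0.57 |
| Simplex, antiviral | 0 | 12 × 0.25 = 3.0 |

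Since p(1 − p) cannot exceed 0.25, no zoster row loses more than 1.2 × 0.25 = 0.3 on these assumptions. Zoster interruption is little exposed in any case, because Protocol Table JAIN.4 holds drug for symptomatic zoster. The 3.0 is out of a true simplex antiviral row of 18 × 0.5 + 12 × 0.75 = 18.

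**3. How sensitive is the 3.0?**

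- If half of recurrent patients have matching events: 1.5.
- If ties always favour the event with the feature: 12 × 0.58 × 0.25 = 1.74; with both, 0.87.
- If a patient's events always match: 0.
- Middle case (10% affected, 30% recurrent, so 6 patients; half with matching events): 6 × 0.125 = 0.75 of a true row of 14 × 0.5 + 6 × 0.625 = 10.75.
- Three events per recurrent patient at the high end: (0.875 − 0.5) × 12 = 4.5.

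**4. Pooled baricitinib.** The planned arms give at least 100 + 200 + 100 = 400 patients, so the figures double. At the high end, a 5% simplex feature loses 24 × 0.0475 = 1.14 patients and simplex antiviral use 24 × 0.25 = 6.0; the middle case for antiviral use is 1.5. In the 2-mg arm alone, a simplex feature carried by 10% of events would lose up to 12 × 0.09 = 1.08.

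**The case against.** The strongest defence is that this is an explicit, prespecified index-event convention. Every row describes the same event, so severity, action taken, treatment and outcome can be read together. Any-event counting gives that up: antiviral use might come from one episode and outcome from another. This is a real trade-off. It supports keeping zoster outcome on the most severe event, but not reading the other rows as patient counts.

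Second, much is reported elsewhere. SAEs, AE-related interruptions and discontinuations, and serious infections are all counted by preferred term without this rule, and several have full listings. This stands, and it leaves antiviral use as the main row without a documented any-event count. The planned infection listing may show it, but its content is not in the documents. A listing would not correct the tabulated count in any case.

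Third, every rate in the calculation is assumed, and the top figure stacks unfavourable choices. That also stands, so only the direction is firm. Table titles or footnotes could also tell readers that the rows describe one selected event, but the table shells are not available.

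A reader might further infer that the zoster classification (localised, multidermatomal, disseminated, complicated) is understated in the same way. The SAP does not say that the rule governs the classification; it says that every zoster case is classified at medical review. That inference is not supported.

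**Conclusion.** The point holds as a minor, descriptive one. As written, the four yes/no rows in both tables can understate the number of patients with the feature and cannot overstate it. On the assumed rates the loss is probably under one patient per randomised arm in most scenarios. It is larger in the pooled baricitinib group and zero if a patient's events always agree. The antiviral row, chiefly for simplex, is the most exposed; other rows could also reach a whole patient if the feature were commoner or the group larger.

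Two stronger readings are not supported. The plan does not hide serious or drug-stopping herpes events, because the SAE, discontinuation, interruption and serious-infection summaries pick them up. Nor would a gap between a herpes seriousness row and the serious-infection summary reveal the rule. That summary covers all infections by preferred term, while the simplex table pools narrow and broad terms, so the two need not agree anyway.

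**What to change.** In both the Herpes Zoster and Herpes Simplex parts of section 6.13.4.6, add a sentence: for seriousness, temporary interruption, discontinuation and antiviral treatment, a patient counts as yes if any treatment-emergent event qualifies. Keep maximum severity, and for zoster the outcome, on the most severe event, and label those rows accordingly. Add a footnote with the number of patients who had two or more events, so that readers can see how far the choice matters.

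The cost is one sentence per subsection and minor reprogramming, with no new data. There are two downsides. The rows will no longer all describe one event. Also, SAP Version 5 comes after the Week 24 analysis, and its change logs for Versions 3 to 5 list no change to this section, so tables from earlier locks would need a note or a rerun to stay comparable.
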